12 IMMUNOLOGICAL RESPONSE EVALUATIONS

Immunological response evaluations for baseline values will be conducted on PBMCs collected at the time of the initial leukapheresis sample. Immunologic response evaluations will also be performed from peripheral blood obtained prior to select vaccinations. The primary comparison for immunologic endpoints will be baseline response (pre-leukapheresis or P1) compared to response post vaccine #3 (post-leukapheresis or P2). Our previous studies demonstrated a significant increase in immunologic responses in vaccinated patients that peaked after the third vaccine in most subjects. A comparison of pre-therapy lymphocyte function to additional vaccine time points may be conducted on an exploratory basis. Arms 1 and 2 (pp65-shLAMP RNA-pulsed DCs and pp65-fLAMP RNA-pulsed DCs) will be analyzed separately for immunologic endpoint comparisons. Studies examining DNA vaccines using full-length LAMP1 fusion antigens compared to truncated versions of the LAMP protein have demonstrated that increased antigen expression, secretion of LAMP fusion proteins, enhanced antibody titers, increased cytokine release by CD4+ and CD8+ T cells, improved central memory T cell differentiation, and enhanced

polyfunctional T cell responses, all were dependent on full-length LAMP1 fusion antigens(Godinho, Matassoli et al. 2014). Truncated LAMP fusions that did not contain the luminal domain of LAMP were much less efficient in this wide spectrum of immunologic analyses. As a primary biologic analysis and secondary endpoint of this study, we will compare the immunologic responses in patients vaccinated with CMV pp65-fLAMP RNA-pulsed DCs (Arm 1) to patients vaccinated with CMV pp65-shLAMP RNA-pulsed DCs (Arm 2) across this spectrum of responses.

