7 STUDY RATIONALE

We have demonstrated in murine models that DCs loaded with tumor-specific antigens in the form of peptides or RNA can induce potent and specific humoral and cell-mediated immune responses that are effective against murine intracerebral (i.c.) tumors, including a syngeneic murine astrocytoma, without inducing autoimmunity(Heimberger, Crotty et al. 2000; Heimberger, Archer et al. 2002; Heimberger 2003; Mitchell, Cui et al. 2011). Our previous clinical experience has also shown that DC vaccines in combination with standard of care radiation therapy and chemotherapy are capable of generating potent, tumor-specific immune responses and clinical radiographic responses in patients with MGs. We and others have also shown that antigens derived from CMV are contained within MGs and may serve as potent and specific immunotherapy targets. Vaccination and adoptive T-cell strategies targeting CMV in humans in other contexts, including the targeting of lesions within the CNS, have been safe and effective. We have also shown that DCs generated from patients with GBM and loaded with pp65-LAMP mRNA are capable of generating CD4+ and CD8+ T-cells that produce IFN- γ and kill malignant astrocytes infected with CMV in an antigen-specific fashion. We have found that TILs isolated from these patients are significantly enriched for T-cells that specifically recognize CMV antigens, suggesting that this

response may be important in the biology of these tumors. We have recently demonstrated that fusion of the immunodominant antigen CMVpp65 to full-length LAMP targeting protein enhances activation and expansion of CMV-specific T cells *in vitro*. TMZ has recently shown efficacy in some patients with newly-diagnosed GBM and is now frequently given to these patients during initial RT. Therapeutic TMZ induces a profound lymphopenia, however, that may inhibit anti-tumor vaccination. With these observations in mind, we are now proposing to determine the immunologic and clinical effects of CMV-specific vaccination after therapeutic TMZ-induced lymphodepletion with GM-CSF and with Td skin preparations in patients with newly-diagnosed GBM.

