All patients will undergo repeat leukapheresis 2 to 4 weeks after vaccine #3 for PBMCs to generate additional DC vaccines and for immunologic monitoring with specific assessment of baseline antigen-specific cellular and humoral immune responses. TMZ cycle 2 will occur 24 hours to 1 week after repeat leukapheresis. Patients may undergo additional leukapheresis, if needed, to generate up to 10 DC vaccines as outlined in section 9.6., Removal of PBMCs by Leukapheresis.

Patients will then be vaccinated monthly in conjunction with subsequent TMZ cycles every 5(+/- 1) weeks for a total of 6 to 12 cycles after RT as per guidelines defined in recent phase III clinical trial evaluating TMZ regimens in patients with GBM (RTOG 0525). Vaccines will be given on day 22-24 of each TMZ cycle. Patients will continue with monthly vaccinations until a total of 10 vaccines have been administered or until tumor progression (whichever comes first).

All patients will undergo vaccine site pretreatment with Td (1 Lf) or saline (depending on randomization arm) 6-24 hours prior to Vaccine #3, #6, and #9. At vaccine #3, patients at the UF site will undergo MRI/MRS imaging of inguinal vaccine-site draining lymph nodes before vaccine site pretreatment, 48 hrs post vaccination, and 5 to 7 days post vaccination (optional). Peripheral blood and urine samples will be collected at these time points for soluble biomarker analysis.

Patients who have been enrolled in the study and become ineligible to receive study treatment for reasons other than progression may be allowed to receive vaccines that have been generated for them at the discretion of the PI as outlined in section 9.8 DC or PBMC Vaccination.

Blood for immune monitoring will be collected during initial leukapheresis, prior to vaccines 1-3, during MRI/MRS imaging time points surrounding vaccine #3, during the second leukapheresis, prior to vaccine 4, 7, 10, and at progression if feasible. Peripheral blood will be processed in accordance with **SOP-UFBTIP-126**. Urine samples will be collected at MRI/MRS imaging time points surrounding vaccine #3 and transferred to the UFBTIP laboratory for nMR analysis.

Up to twelve cycles of TMZ may be given if the patient demonstrates continued improvement or stability on radiologic scan, decreased corticosteroid requirement, improvement in performance status, or improvement in neurologic function.

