9.6 Removal of PBMCs by Leukapheresis

Prior to the initiation of TMZ and external beam RT and again 2 to 4 weeks after vaccine #3, subjects will undergo leukapheresis in accordance with **SOP-UFBTIP-131**. Intravenous access will be obtained by placing two large gauge catheters into the antecubital veins bilaterally or by using a dialysis-type central venous catheter that will allow for large volume apheresis. In addition to research protocol consent, additional surgical/procedural consent will be obtained for placement of the central venous catheter by the surgeon/proceduralist. Placement of this special catheter may require use of fluoroscopy. The procedure will be conducted using the COBE® Spectra™ Apheresis System (or equivalent). A sample of each leukapheresis product will be used for immunologic monitoring.

Subjects may undergo additional leukapheresis, if needed, to generate up to 10 DC vaccines. Additional leukapheresis procedures may be performed at anytime at the discretion of the PI to

limit treatment interruption/delay as much as possible. When feasible, additional leukapheresis should be scheduled no earlier than 1 week following DC vaccination and prior to the following TMZ cycle. After the leukapheresis, TMZ cycle may occur as scheduled.

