15.2 Sample Size Justification for Vaccine Comparison

The primary focus of this trial will be to assess the worthiness of pp65-LAMP mRNA DC vaccine for further investigation by comparing overall survival (OS) between the active treatment group (Arms 1 and 2 combined) and the control group (Arm 3). Because this test for efficacy will be made within the framework of a phase II trial, we have constrained sample size requirements to yield adequate power to detect a clinically relevant improvement in OS at the expense of the false positive rate (α -level or Type I error rate). Adopting guidelines proposed by Ratain and Sargent (2009) and Rubinstein et al (2005), our proposed sample size of $40 + 40 = 80$ patients in the treatment group and 40 patients in the control group will allow detection of a clinically relevant improvement in the median OS time of the treatment group with 90% power at a one-sided α -level of 0.2.

In determining the effect size that can be detected by our proposed sample size, we considered using as a control reference level the median OS estimate of 14.6 months (95% CI: 13.2 to 16.8) reported by Stupp et al (2005) for patients receiving radiotherapy plus TMZ (RT+TMZ) for newly-diagnosed GBM (40% of patients in the Stupp trial were grossly resected). In the Stupp trial, randomization occurred prior to any post-surgical treatment, and the timing of randomization in our study will be similar. However, in our study, patients will not begin to experience potential differential effects due to treatment until after their first vaccination, which will occur approximately 15 weeks after randomization. To determine an appropriate control reference level for median OS for an index day 15 weeks after randomization, we carefully transferred the coordinates of multiple points along the Stupp RT+TMZ OS curve into a statistical software package. We determined that median OS relative to a starting time 15 weeks after the Stupp index day would be 13.8 months. We also observed that RT+TMZ OS times appeared to approximately follow a Weibull distribution with a shape parameter = 1.20, indicating a slightly accelerating baseline hazard function. Upon examining in a similar manner the RT+TMZ OS curve reported in the paper by Gilbert et al (2013), we also observed approximately Weibull-distributed OS times with shape parameter = 1.16.

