15.3.2 Secondary Biological Objectives

We will estimate within-patient changes in immune response (ELISPOT, cytokines array, flow cytometric analysis and NK cell activity) from baseline to vaccine #3 and compare these changes between treatment and control groups using the Wilcoxon rank sum test. To assess the effect of these changes in immune response on OS and PFS subsequent to vaccine #3, we will conduct a landmark analysis within the framework of Cox proportional hazards models of post-baseline OS and PFS. These models will incorporate Indicators for treatment arm, change in immune response parameters from baseline to vaccine #3, interaction between treatment arm and immune response changes, and potential confounders.

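### The primary immune change starts before chemoradiation, so it cannot be attributed to vaccination alone; adjust for both pre-vaccine samples instead of testing the raw change

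*Combined protocol and SAP*

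**What the plan says.** Section 12 fixes the baseline sample: "Immunological response evaluations for baseline values will be conducted on PBMCs collected at the time of the initial leukapheresis sample". It then names the main contrast: "The primary comparison for immunologic endpoints will be baseline response (pre-leukapheresis or P1) compared to response post vaccine #3". Section 9.6 gives the timing of both samples: "Prior to the initiation of TMZ and external beam RT and again 2 to 4 weeks after vaccine #3, subjects will undergo leukapheresis". Section 15.2 places the first vaccination on the calendar, "which will occur approximately 15 weeks after randomization".

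Section 15.3.2 uses the resulting change twice. It compares within-patient changes between treatment and control groups with the Wilcoxon rank sum test. It also enters "change in immune response parameters from baseline to vaccine #3" in landmark Cox models of OS and PFS, with treatment arm, an arm-by-change interaction and unnamed potential confounders.

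A later unvaccinated sample exists. Section 9.1 says: "Blood for immune monitoring will be collected during initial leukapheresis, prior to vaccines 1-3", and Section 10.4 lists the draw before vaccine 1 separately. Neither Section 12 nor 15.3.2 makes it a reference or a covariate. The only other comparisons Section 12 allows are exploratory and again start from pre-therapy function.

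The terms are not used consistently. The synopsis and Section 9.1 describe the second leukapheresis, after vaccine 3, as serving "immunologic monitoring with specific assessment of baseline antigen-specific cellular and humoral immune responses". Section 12 ends the interval at P2; Section 15.3.2 ends it at vaccine #3.

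**The concern.** Between P1 and vaccine 1 every patient is scheduled for radiotherapy with daily TMZ and then a first adjuvant TMZ cycle. The protocol's own rationale (Section 7) says: "Therapeutic TMZ induces a profound lymphopenia, however, that may inhibit anti-tumor vaccination". Section 6.8 adds that lymphopenia drives rapid proliferation of naive and memory T cells, and Sections 6.8 and 6.9 that TMZ may preferentially deplete regulatory T cells, which are in the Section 12.2 flow panel. Immune readouts can therefore move between P1 and P2 without any vaccine.

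Two uses are affected. The within-patient change that Section 12 calls primary cannot be read as a vaccine response. In the landmark model, a change that partly reflects how a patient came through chemoradiation may track prognosis, so its link with survival cannot be read as an effect of the vaccine-induced response. The comparison behind the second secondary objective, full-length against short LAMP, is randomized and stays valid, but carries noise that adjustment would reduce.

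**Working it through.** **1. The plan's own 15 weeks.** Inputs: Appendix A (59.4-60.0 Gy at 1.8-2.0 Gy, five fractions a week, up to 7 weeks), Section 9.1 (cycle 1 starts 4 ± 1 weeks after radiotherapy), Section 9.8 (vaccine 1 on day 22-24).

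- Radiotherapy: 60/2/5 = 6.0 weeks; 59.4/1.8/5 = 6.6 weeks; at most 7.0.
- Start of radiotherapy to vaccine 1: 6.0 + 4 + 21/7 = 13.0 weeks, up to 7.0 + 4 + 23/7 = 14.3 weeks (12.0-15.3 with the ±1 week window).
- With an assumed 1-2 weeks from randomization to radiotherapy, this is about 14-16 weeks. The stated 15 weeks is reproduced.

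**2. Share of the P1-to-P2 interval before any vaccine.** Take P1 to vaccine 1 as about 15 weeks. Vaccines 1 to 3 span two 2-week intervals, 4 weeks (2-6 with windows). P2 follows 2-4 weeks later.

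- P1 to P2: 15 + 4 + 2 = 21 to 15 + 4 + 4 = 23 weeks (19-25 with windows).
- Pre-vaccine share: 15/23 = 65% to 15/21 = 71% (15/25 = 60% to 15/19 = 79% with windows).
- If P1 is as late as the start of radiotherapy: 13.0/21.0 = 62% to 14.3/20.3 = 70%.
- If follow-up is the vaccine #3 visit, as Section 15.3.2 says: 15/19 = 79%.

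**3. TMZ exposure before vaccine 1.** Up to 49 days with radiotherapy (Section 10.3) plus 21 adjuvant days (Section 9.5) = 70 days. Patients aged 70 or over, or with grade 3 or higher hematologic toxicity in chemoradiation, have a 5-day cycle: 49 + 5 = 54. Exposure therefore differs between patients.

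**4. The interval from the pre-vaccine-1 sample to P2.** 4 + 2 = 6 to 4 + 4 = 8 weeks (4-10 with windows). It contains no radiotherapy and no scheduled TMZ, because cycle 2 starts after the second leukapheresis (Section 9.1).

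**5. Precision of the arm comparison (illustration).** The documents give no SD, correlation or power for immune endpoints. Assume unit variance at each time, correlation r between P1 and P2, 40 per arm, a true difference of 0.5 SD, two-sided 0.05 and a normal approximation. Variance is 2(1 − r) for the change score and 1 − r² for ANCOVA on P1. Power = Φ(0.5/√(2 × variance/40) − 1.96).

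| r | Variance, change | Power | Variance, ANCOVA on P1 | Power |
|---|---|---|---|---|
| 0.3 | 1.40 | 47% | 0.91 | 65% |
| 0.4 | 1.20 | 53% | 0.84 | 68% |
| 0.6 | 0.80 | 71% | 0.64 | 80% |

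The variance ratio is 2/(1 + r): 1.54 at r = 0.3 and 1.25 at r = 0.6. This gain needs no new sample.

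**6. Adding the pre-vaccine-1 value.** With r₁ and r₂ the correlations of P1 and pre-vaccine-1 with P2, and r₁₂ the correlation between them, the residual variance is 1 − (r₁² + r₂² − 2r₁r₂r₁₂)/(1 − r₁₂²). If r₂ = r₁r₁₂ this equals 1 − r₁², so the second sample adds nothing. It helps only as far as it predicts P2 beyond P1.

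**The case against.** The strongest reply is that randomization precedes P1 and all arms, including control, receive the same chemoradiation. The shared effect cancels in expectation. This stands: a reader might infer that the arm comparisons are biased, and the documents do not support that.

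A reader might also infer that the pre-vaccine-1 sample should simply replace P1. That does not hold either. It is drawn on about day 22-24, on the 21-day regimen just after TMZ dosing, so a change from it can include the lymphocyte recovery described in Sections 6.8 and 6.9. In the landmark model this would swap one confounder for another. Nor need it be the better predictor: if its correlation with P2 were 0.4 and that of P1 were 0.6, ANCOVA on it alone would give about 68% power, against 71% for the existing change score.

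A third tempting inference credits the new sample with the whole power gain. With correlations of 0.4 for P1 and 0.7 for pre-vaccine-1, moving from the P1 change to ANCOVA on pre-vaccine-1 takes power from 53% to 88%. ANCOVA on P1 alone already reaches 68%, and the rest depends on an assumed correlation.

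Two further points stand in part. The ELISPOT in Section 12.1 plates a fixed number of PBMC and reports per million, so a low lymphocyte count does not enter mechanically, although cell composition and function can. The landmark models do include arm, an interaction and confounders; the interaction asks whether the association differs by arm, but it does not make the change a measure of vaccine response, and the confounders are not named.

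**Conclusion.** The concern holds in a limited form. About two thirds of the primary immune interval (65-71% on the nominal schedule, 60-79% with visit windows) passes before any study vaccine, so neither the within-patient change nor its landmark coefficient can be attributed to vaccination alone. This rests on the schedule and on taking P1 to vaccine 1 as about 15 weeks; it changes little if P1 is later.

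For the arm comparisons the issue is precision. The power figures are illustrative: they rest on assumed correlations, an assumed 0.5 SD difference, near-normal data and all 40 patients per arm supplying samples. They show that adjustment beats the raw change for any r below 1. They do not establish how much the pre-vaccine-1 sample adds. Even a well-adjusted landmark result remains an association.

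**What to change.** In Sections 12 and 15.3.2:

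- **Arm comparisons.** Compare P2 between arms, including full-length against short LAMP, by rank ANCOVA adjusted for both the P1 and pre-vaccine-1 values. Both precede any study vaccine, so both are valid covariates. Make the arm contrast the inference and keep the P1-to-P2 change as descriptive.
- **Landmark model.** Enter P2 with P1 and pre-vaccine-1 as covariates in place of a change from either one alone. Describe the result as an association. If P2 is the follow-up point, the landmark time must not precede the second leukapheresis.
- **Definitions.** State baseline and follow-up once, settle P2 against vaccine #3, and remove the word baseline from the description of the second leukapheresis in the synopsis and Section 9.1.

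The cost is plan wording plus assays of the pre-vaccine-1 sample where these are not already planned; no new visit is needed. That sample is peripheral blood drawn in acute lymphopenia, so yield may be low and some values missing; state how these will be handled. Blood for immune monitoring is also drawn at both leukaphereses, so a like-for-like blood comparison is possible.

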12.1 ELISPOT Assay

[figure not shown]
The ELISPOT assay, our primary assay to detect cellular immune responses is a sensitive detection assay for evaluation of antigen-specific cytokine producing T-cells. The IFN- γ ELISPOT allows for the direct visualization of human γ -interferon cytokine release from a single cell, which has been widely reported to be an indicator of activation of an antigen-specific immune response.

On the day of testing, PBMCs will be thawed quickly, washed, resuspended in R-10 medium and cell counts and viability measured PBMCs (250,000/well) will be stimulated overnight with synthetic peptides consisting of a peptide cocktail derived from human CMV proteins. Single-use aliquots of the peptide pools will be resuspended to a final concentration of 1 μ g/mL for each peptide. Each assay will include PBMC cultured with no peptide or PHA (2.5 μ g/mL, 0.25 μ g/mL) and positive and negative control PBMC for each antigen if available. PBMC are added to duplicate wells of 96-well ELISPOT assay plates coated with mouse IgG1 anti-human IFN- γ monoclonal antibody (MAb) will be incubated overnight at 37°C, 5% CO₂, washed with PBS/Tween 20, incubated with biotinylated mouse IgG1 anti-human IFN- γ MAb for 1 hour at room temperature, washed with PBS, incubated with avidin-peroxidase complex for 1 hour at room temperature, washed, incubated with substrate (3-amino-9-ethylcarbazole) for 4 min at room temperature and spot development stopped by distilled water rinse. Plates will be dried and shipped to Zellnet Consulting (New York, NY) for spot enumeration by automated analysis with a Zeiss KS ELISPOT system. Results will be expressed as the mean spot-forming cells (SFC)/10⁶ PBMC after subtraction of counts from cells cultured with no peptide.

12.2 Polyfunctional T cell Responses, T cell Phenotype, and Other Type of Immune Cell Phenotype

The laboratory of UFBTIP will conduct a flow cytometric analysis that aims to quickly detect the activation of T cells through CD69 and exhaustion via PD-1. A 13-color assay will be used to monitor the polyfunctional immune response of patients' CD4 and CD8 cells. The analysis will also include an examination of the phenotypic distribution of T cells that respond to the assay, including naive, effector, central memory, effector memory, and terminal effector cells. Additionally, the same panel will be used to analyze regulatory T cells (identified as CD3+CD4+CD25+FoxP3+), natural killer cells (CD56+), natural killer T cells (CD56+CD3+), invariant natural killer T cells (CD56+CD3+TCR-va24+), and cell viability (measured through the Live/Dead Fixable Blue Viability Assay) (as seen in Figure 13).

Immediately preceding select vaccinations peripheral blood will be drawn into vacutainer tubes containing ACD. PBMC will be separated by density gradient centrifugation on ficoll-Hyopaque and then cryopreserved until the day of immune monitoring operation..

12.3 Multiplex Cytokine Quantification

The UFBTIP laboratory will perform a Multiplex cytokine analysis to detect multiple cytokines secreted by lymphocytes. This analysis will use a multiplex kit on the Meso Scale Discovery platform to simultaneously examine Type 0,1,2, and 3 cytokines (IFN- γ , IL-1 β , IL-2, IL-4, IL-6, IL-8, IL-10, IL12p70, IL-13, and TNF- α) secreted by T cells. Prior to select vaccinations, peripheral blood will be drawn into vacutainer tubes containing silicone and micronized silica particales (SST) to isolate patient serum. This serum will be cryopreserved until the day of the Multiplex cytokine assay.

12.1 Single Cell Gene Expression and Immune Profiling For Monitoring Changes in Glioblastoma Patients with Sustained Radiographic Response to CMV pp64-LAMP RNA-Pulsed Dendritic Cell-Based Vaccines.

The application of single cell sequencing as a novel immune monitoring platform can be used to identify the molecular mechanisms of immune response to dendritic cell- based vaccines, trace the cell types and states involved, and uncover novel biomarkers for immunotherapy. We will perform

single-cell RNA Seq analysis of longitudinal peripheral blood mononuclear cells (PBMCs) in selected patients.

Cell preparation: Frozen cell vials with PBMCs collected at different time points following DC vaccination of selected ATTAC patients will rapidly be thawed in a 37°C water bath. Thawed PBMCs will be washed and filtered with a cell drainer. Cells will be collected by centrifugation and subsequently counted with hemocytometer. For Single cell RNA-seq, single cell suspension will be loaded onto Chromium Controller according to the manufacturer's specifications and TCR-seq libraries will be prepared via PCR amplification with primers specific to the TCR and for 5' gene expression library construction. Pre-processing of scRNA-seq data will be performed using specific software for identification of cell types.

